Methodology: This is a randomised, phase III, multicentre, double-blind, placebo-controlled efficacy and safety study of oral darolutamide in patients with nmCRPC who are at high risk for developing metastatic disease. The study has a design of 2 parallel groups and consists of 2 periods: a study treatment period and a follow-up period. All eligible patients will be randomised to receive darolutamide 600 mg twice daily or placebo in a 2:1 ratio in a double-blind manner. Randomisation will be stratified by PSA doubling time (PSADT; ≤ 6 months vs. > 6 months) and use of osteoclast-targeted therapy (yes vs. no). All patients will visit the study centre at day 1, day 15, day 29, week 16, and every 16 weeks thereafter. CT/MRI and bone scans will be obtained at baseline and every 16 weeks until metastasis. Absence or presence of metastasis will be confirmed at baseline and during the double-blind treatment phase by a blinded independent central reading. Changes identified by central reading must be confirmed with anatomic imaging (CT/MRI or x-ray). Upon central confirmation of metastasis, the patient must be withdrawn from the study treatment and the patient will be followed every 16 weeks for secondary and additional variables (OS, first SSE, pain progression, first prostate cancer-related invasive procedure, initiation of subsequent antineoplastic therapy, initiation of cytotoxic chemotherapy, initiation of opioid use for pain, and changes in ECOG performance status and QoL) until the end of the study by visit or telephone contact. Patients initiating a prohibited therapy before confirmation of the metastasis during the double-blind part should discontinue study treatment and patients will be followed only for survival status until the end of the study. The double-blind part is planned to be continued until the total number of MFS events have been reached at approximately 385 events.		

Once the study results are available, and if they support a positive benefit/risk assessment for darolutamide in the study by judgment of the Sponsor (considering feedback from the study steering committee and/or health authorities), those patients who are on study treatment (darolutamide or placebo) will be offered the opportunity to receive darolutamide through open-label treatment in this study.

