6.6.2.3 Physical examination

Physical examination will be performed and weight will be measured at all visits except at day 15 visit. Height will be recorded at screening only.

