#### **Adverse events within SOC Cardiac disorders**

The following additional tables for TEAEs by history of cardiac disorders will be created:

- for the subgroup of patients with present medical history in the SOC ‘Cardiac history’,
- for the subgroup of patients without present medical history in the SOC ‘Cardiac history’.

In all tables, results will be shown by treatment group.

Incidence proportions of the TEAEs in the system organ class (SOC) ‘Cardiac disorders’ will be presented by HLGT, HLT, PT and worst CTCAE grade.

Interval specific and cumulative incidence proportions for TEAEs will be presented for the HLGTs Cardiac arrhythmias, Coronary artery disorders, and Heart failures.

In addition, Exposure adjusted treatment-emergent AE (fracture, weight decrease, cardiac disorders, fall) per 100 patient years will be created for the treatment groups:

- Darolutamide – double-blind period
- Darolutamide – double-blind and open-label periods
- Placebo – double-blind period

Below selection will be used:

- Bone fractures: HLT: Fractures and dislocations NEC (without PTs: Joint dislocation, Joint dislocation pathological), HLT: Limb fractures and dislocations (without PT: Radial head dislocation), HLT: Pelvic fractures and dislocations, HLT: Skull fractures, facial bone fractures and dislocations, HLT: Spinal fractures and dislocations (without PT: Dislocation of vertebra), HLT: Thoracic cage fractures and dislocations (without PT: Dislocation of sternum)
- Weight decrease: MLG weight decrease
- Cardiac arrhythmia: HLGT cardiac arrhythmias
- Coronary artery disorders: HLGT coronary artery disorders
- Heart failures: HLGT Heart failures
- Fall: PT Fall and PT Accident

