## 6.5 Safety

No formal statistical tests will be done for the safety endpoints. All analyses for safety will be performed in the SAF population.

An updated analysis of safety events will be performed as of the final OS analysis.

Specific tables of adverse events will be displayed by following subgroups:

- Age (years) :<65, 65 - 74, 75 - 84, ≥85,
- Geographical region (North America, Asia Pacific, ROW).
- Renal function - eGFR at baseline (normal vs.mildly impaired vs. moderately impaired, severely impaired and end stage renal disease) (for calculation see Section 6.1.2),
- Hepatic impairment at baseline (normal vs mild vs moderate and severe impairment) (for calculation see section 6.1.2),
- Concomitant statin use (no vs. yes), to be determined by concomitant medication (see Appendix 9.9).

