Interval specific and cumulative event rates for treatment-emergent adverse events (for AE with at least a 5% total incidence rate (any grade)).

Subgroup analyses will be performed for TEAEs. Tables showing differences of at least 5% points in incidence proportions between any of the subgroup categories will be produced.

Following treatment-emergent adverse events are considered as special topics:

- Bone fracture (selected using HLT: Fractures and dislocations NEC (without PTs: Joint dislocation, Joint dislocation pathological), Limb fractures and dislocations (without PT: Radial head dislocation), Pelvic fractures and dislocations, Skull fractures, facial bone fractures and dislocations, Spinal fractures and dislocations (without PT: Dislocation of vertebra), Thoracic cage fractures and dislocations (without PT: Dislocation of sternum))
- Fall (selection of MLG Fall (only PT Fall))
- Seizure (selection of MLG Seizures)
- Fatigue (selection of MLG decreased general strength and energy, selection of PT Lethargy, Malaise, Chronic fatigue syndrome)
- Weight decreased (selection of MLG Weight decreased)

Following tables will be created for the TEAE of special topics

- Treatment-emergent AEs
- Treatment-emergent AEs leading to study drug withdrawal
- Treatment-emergent AEs leading to dose reduction
- Treatment-emergent AEs leading to drug interruption
- Treatment-emergent SAEs

Incidence of TEAEs of special topics will be displayed for the subgroup of concomitant statin use.

Fracture events will be described by a cumulative incidence plot of fracture. A summary of treatment-emergent fracture by bone sparing agent use (for selection of bone sparing agent see Appendix 9.14) at study entry will be provided. Association with weight decrease will be presented by histogram of fracture events by patient weight change (the weight collected closest to the start of fracture will be considered and compared to baseline weight).

A listing will be generated for patients with fall treatment-emergent events with syncope and/or loss of consciousness (using the MLG Syncope).

An overview of patients at risk for developing an AE seizure will be tabulated by displaying medical history.

Listing of non-treatment-emergent AEs will be created.

Incidence of post treatment non-treatment-emergent AEs will be tabulated.

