### 6.5.6 Other safety measures

For each treatment group, vital signs (i.e. blood pressure, heart rate, weight and BMI) will be tabulated and summarized by visit for observed values and changes from baseline using descriptive statistics, as appropriate. If more than one baseline assessment was collected, the most recent one will be used. If several assessments are performed on the same day (without timing information) the average of the values will be considered.

In addition to descriptive analysis box plots will be created.

For weight parameter a graph representing mean changes in weight from baseline by visit will be created.

Outlier analyses will be conducted using the following limits:

- low systolic blood pressure:  $\leq 90$  mmHg and a decrease of  $\geq 20$  mmHg
- high systolic blood pressure:  $>190$  mmHg and an increase of  $\geq 20$  mmHg
- low diastolic blood pressure:  $\leq 50$  mmHg and a decrease of  $\geq 20$  mmHg
- high diastolic blood pressure:  $> 105$  mmHg and an increase of  $\geq 20$  mmHg
- low heart rate:  $< 50$  bpm and a decrease of  $\geq 15$  bpm
- high heart rate:  $> 120$  bpm and an increase of  $\geq 15$  bpm

The number and percentage of patients with outlying values will be tabulated by treatment group and time interval.

No subgroup analyses will be performed.

Unscheduled vital signs data will be listed (Section 16 of the CSR) but will be included in the summary tables.

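### The fracture-by-weight histogram contains fracture events only and may use a weight taken after the fracture, so on its own it cannot show the association it is meant to present

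*SAP*

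**What the plan says.** Bone fracture and weight decreased are two of the five special safety topics in SAP v4.2 section 6.5.2. To relate them, the SAP plans one display: "Association with weight decrease will be presented by histogram of fracture events by patient weight change". The weight to be used is defined in the same sentence: "the weight collected closest to the start of fracture will be considered and compared to baseline weight". Supplement 7, section 6.5.2, repeats both parts unchanged after Table 6–1.

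On when weight is measured, protocol section 6.6.2.3 says: "Physical examination will be performed and weight will be measured at all visits except at day 15 visit". The visit pattern is in the protocol synopsis: "All patients will visit the study centre at day 1, day 15, day 29, week 16, and every 16 weeks thereafter".

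Other planned outputs that involve weight or fracture:

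- SAP v4.2 section 6.5.6 summarises vital signs, including weight, by visit and treatment group with change from baseline, adds box plots, and states: "For weight parameter a graph representing mean changes in weight from baseline by visit will be created". Supplement 7 keeps the by-visit summaries.
- SAP v4.2 section 6.5.2 plans a cumulative incidence plot of fracture, fracture by use of bone sparing agents at study entry, and event rates per 100 patient-years for special topics.
- Supplement 7 adds "Exposure adjusted treatment-emergent AE (fracture, weight decrease, cardiac disorders, fall) per 100 patient years", by treatment group, and a joint summary of falls and fractures.

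Section 6.5 gives the status of all of this: "No formal statistical tests will be done for the safety endpoints".

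**The concern.** There are two separate problems.

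First, a weight change measured at the start of a fracture exists only for a man who has had a fracture. The histogram therefore shows how fractures are spread over weight change. It does not show how weight change is spread among men, or patient-time, without a fracture. Whether weight loss goes with fracture depends on the comparison of the two, and the sentence names no comparator, denominator or patient-time. Splitting the histogram by arm would not supply one.

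Second, the nearest weight is not required to come before the fracture, and no maximum distance is set. If a man loses weight after a fracture and the next visit is the nearer one, that later loss enters the display as the weight change that accompanied the fracture.

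What is at stake is how one safety display is read. A cluster of fractures among men with weight loss could be taken as a link when it only mirrors the weight change of the whole population, or follows from the fractures themselves. A real link could equally be missed.

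**Working it through.** The documents state no figure on this point, so there is none to reproduce. The calculations below are illustrations; each assumption is marked.

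**Inputs from the documents.** Scheduled weights fall on day 1, day 29, week 16 (day 113) and every 16 weeks (112 days) after that. The nearest weight is used, in either direction. Visit windows from week 16 on are ±7 days.

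**1. A histogram of fractures alone does not fix the association.** Let c be the share of fractures in a weight-loss band and f the share of patient-time in that band. The rate ratio, band against the rest, is (c/f) / ((1−c)/(1−f)). Take c = 0.20 (assumed):

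| f (assumed) | Calculation | Rate ratio |
|---|---|---|
| 0.20 | (0.20/0.20) / (0.80/0.80) | 1.0 |
| 0.10 | (0.20/0.10) / (0.80/0.90) | 2.25 |
| 0.05 | (0.20/0.05) / (0.80/0.95) | 4.75 |

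The histogram gives c and not f, so the same picture fits all three rows.

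**2. How often the nearest weight is a later one.** For a fracture at a uniformly distributed time between two visits (assumed), the later visit is the nearer one in half of cases. The longest lag is half the gap:

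- between 16-week visits: 112/2 = 56 days, about 8 weeks;
- between day 29 and day 113: 84/2 = 42 days, about 6 weeks;
- if the visit windows stretch a 16-week gap to 112 + 14 = 126 days: 63 days.

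A simulation of uniform fracture times over day 1, day 29 and ten 16-week visits agrees: 50.0% take a later weight, with a mean lag of 26.9 days and a maximum of 56.0 days. Protocol section 6.1.4 allows weight at unscheduled visits. A visit prompted by a fracture would raise the share, though at a short lag.

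**3. What a later weight could do.** Assume no relation between weight change and fracture beforehand, weight change with SD 4 kg, and a post-fracture loss reached linearly over 28 days. None of these comes from the documents. The share of fractures shown with a loss of at least 4 kg is then:

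| Assumed loss after fracture | Nearest weight | Last weight before fracture |
|---|---|---|
| 0 kg | 15.8% | 15.8% |
| 2 kg | 21.1% | 15.8% |
| 4 kg | 27.9% | 15.7% |

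The rise comes only from the choice of weight.

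**4. Does another output supply the link?** The by-visit weight summaries cover all patients, are not split by fracture status and are not matched to the time of fracture. The exposure-adjusted rates treat fracture and weight decrease as separate events. Fracture is crossed with bone sparing agents and, in Supplement 7, considered jointly with falls, but not with weight change. The safety subgroups in SAP v4.2 section 6.5 do not include weight change. No other planned output relates fracture to weight change within patients.

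**The case against.** The strongest reply is that a reference is planned. Weight change by visit and arm, with box plots and a graph of means, shows how the whole population's weight moved, and a reader can set the histogram beside it. This stands in part. A reader might infer that nothing in the plan bears on the association at all, and the documents do not support that. But the background is rough: it includes the fracture patients, is indexed by visit and not by time of fracture, and gives no fracture rate by weight change.

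A second reply is that the display is descriptive, with no hypothesis or test. That is correct and limits the weight of the point. A descriptive display should still describe what it is labelled as.

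Third, the shares, the post-fracture losses and the SD are assumed, and the documents do not say that fractures lead to weight loss. This stands in full. A reader might infer that the histogram will show a false link or reverse causation. The documents support only that the rule leaves this possible.

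Fourth, the nearest weight is fresher: at most about 8 weeks away between regular visits, against up to 16 weeks for the last prior weight. That is a real trade-off, but freshness does not repair an uncertain order of events.

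**Conclusion.** The point holds in a limited form. The planned display contains fracture events only and on its own gives no denominator, so the association it is meant to present cannot be read from it without a comparator. This follows from the SAP's wording and needs no numerical assumption.

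The nearest weight may also come after the fracture: about half the time between 16-week visits, up to about 8 weeks later, and up to about 6 weeks later between day 29 and week 16. The half rests on uniformly timed fractures and scheduled visits. Any loss after the fracture could then appear as associated loss; its size is not known from the documents.

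A reader might go further and infer that the fracture findings in general are unreliable. They are not affected: cumulative incidence, exposure-adjusted rates and the between-arm fracture comparison do not use this weight. Nor are MFS or alpha touched. This is a minor improvement to one descriptive safety display.

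**What to change.** In SAP v4.2 section 6.5.2 and in Supplement 7:

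- Use the last weight on or before fracture onset, with a stated maximum gap beyond which weight change counts as missing.
- Tabulate the first-fracture rate per 100 patient-years by time-updated weight-change band and arm in the SAF. Fix the bands in advance, for example loss of 5% or more, smaller loss, and stable or gain.
- As a minimum, show the histogram beside the time-matched weight-change distribution of all patients.

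The cost is a small additional table, which does need time-updated patient-time, and an older weight, normally up to 16 weeks before the fracture.

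One gap must be settled first. For placebo patients crossing over to open-label treatment, protocol Table 4 lists no physical examination or weight, whereas section 6.6.2.3 has weight at every visit except day 15. If Table 4 is what was followed, the last weight for these men could be the one from the start of open-label treatment visit (section 6.1.2.5), and the 16-week limit would not hold. The two passages must be reconciled, or the analysis limited to the double-blind period.

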### 6.5.3 Deaths and Serious Adverse events

Serious adverse events (SAE) will be classified using the National Cancer Institute (NCI) Common Terminology Criteria Adverse Event (CTCAE), version 4.03 and MedDRA version 20.0 or most recent version

- Treatment-emergent SAEs
- Treatment-emergent SAEs leading to study drug withdrawal
- Treatment-emergent SAEs leading to dose reduction
- Treatment-emergent SAEs leading to drug interruption
- Treatment-emergent SAEs leading to dose reduction and/or drug interruption
- Treatment-emergent drug-related SAEs
- Listing of treatment-emergent SAEs
- Listing of non-treatment-emergent SAEs

The incidence of deaths in the study and especially deaths up to within 30 days of last dose of study drug will be summarized by each treatment group and cause of death. All deaths up to within 30 days of last dose of study drug will be listed by patient with start and stop date of study medication, date of death, and cause of death. All deaths beyond 30 days after last dose of study drug will be displayed in a separate listing.

### 6.5.4 Clinical laboratory data

Descriptive statistics (number of observations, mean, standard deviation, minimum, median and maximum values) will be presented for clinical laboratory tests (hematology, clinical biochemistry and urinalysis), their changes from baseline (including baseline value), and their percent changes from baseline by treatment group at applicable visits.

Hematological and biochemical laboratory values will be graded based on NCI CTCAE version 4.03. CTCAE severity grading for laboratory abnormalities are based on applicable laboratory threshold values outlined in NCI CTCAE v4.03. It should be noted that in the present analysis of those laboratory parameters for which additional clinical information potentially can also influence the toxicity grade, this clinical information is in general not available and only the laboratory measurements are used for grading.

Any additional specific handling of the NCI CTCAE v4.03 toxicity grading assignments will be noted in the footnotes of the corresponding tables as applicable per the data collection in the study.

- In the event of overlapping CTCAE criteria ranges for specific lab tests, the algorithm assigns the worst grade
- If calcium type is not recorded (i.e. only “calcium” is recorded), then grading is done as if the calcium is total calcium. “Calcium corrected” is computed from total calcium and serum albumin (if  $\leq 4.0$  g/dl) from the same time point based on CTCAE v3.0 guidance. If serum albumin (if  $\leq 4.0$  g/dl) from the same time point is not available or if “calcium, unspecified” was collected then grading is done as if the calcium is “corrected calcium.”
- Results with special characters (such as “>” and “<”) are not graded.

The frequency of laboratory abnormalities regarding hematology, coagulation panel, clinical chemistry, and urinalysis will be tabulated by treatment group. Worst grades for hematological and biochemical toxicities will be calculated according to CTCAE, version 4.03 based on laboratory measurements, and will be summarized by treatment group and NCI CTCAE v4.03 category and worst grade.

Clinical laboratory toxicities during treatment including a period of 30 days after last dose of treatment will be considered as “treatment-emergent.

### 6.5.5 12-Lead ECG, QTc

Analyses of ECG and QTc will be performed on the SAF population; no subgroup tables will be created.

Corrected QT (QTc) will be calculated using Bazett's (QTcB) and Fridericia's (QTcF) formula.

Standard 12-lead ECGs will be performed in a supine position after at least 10 minutes rest. Three consecutive 12-lead ECG recordings will be performed within approximately 5

minutes at screening and on day 1 visit before the first study treatment administration, at other visits, 12-lead ECG will be obtained once.

An ECG with a QTcF > 500 ms should be confirmed by a second ECG taken 1-2 hours later.

Descriptive statistics including arithmetic mean, SD, median, minimum, and maximum will be presented for the following ECG parameters: HR, RR, PR, QT, QRS, QTcB and QTcF. Parameters will be summarized for actual results and the change from baseline for the safety analysis set by treatment group at each scheduled visit. Baseline for 12-lead ECG will be mean of separate recordings. Similarly, post baseline values of 12-lead ECG for patients will be mean of separate recordings.

Mean time courses +/- one standard deviation will be displayed graphically.

The last non-missing average value before the first study drug intake will be considered as "baseline" data.

If several assessments are performed on the same day (without timing information) the average of the values will be considered.

In case, timing of ECG is missing at day1 then screening assessment will be considered as baseline data.

The number and percent of patients with absolute QTc interval prolongation or QTc increase from baseline will be defined and summarized by treatment arms. The criteria are:

QTc prolongation: QTc interval > 450 msec, QTc interval > 480 msec and QTc interval > 500 msec.

Increase from baseline in QTc interval: QTc interval increases from baseline > 30 msec and QTc interval increases from baseline > 60 msec.

The number and percent of patients with new clinically significant abnormalities on ECGs per the investigator's assessment at post-baseline time points will be summarized by treatment arms.

ECG data will be presented in a listing. Values with QTc interval > 450 msec, > 480 msec, and >500 msec, and change from baseline in QTc interval >30 msec and >60 msec will be flagged. In addition, abnormalities or clinically significant abnormalities found in the 12-lead ECGs at each scheduled time point will be provided in a listing.

ECG data collected under unscheduled visit will be included in the analyses.

### 6.5.6 Other safety measures

For each treatment group, vital signs (i.e. blood pressure, heart rate, weight and BMI) will be tabulated and summarized by visit for observed values and changes from baseline using descriptive statistics, as appropriate. If more than one baseline assessment was collected, the most recent one will be used. If several assessments are performed on the same day (without timing information) the average of the values will be considered.

In addition to descriptive analysis box plots will be created.

For weight parameter a graph representing mean changes in weight from baseline by visit will be created.

Outlier analyses will be conducted using the following limits:

- low systolic blood pressure:  $\leq 90$  mmHg and a decrease of  $\geq 20$  mmHg
- high systolic blood pressure:  $>190$  mmHg and an increase of  $\geq 20$  mmHg
- low diastolic blood pressure:  $\leq 50$  mmHg and a decrease of  $\geq 20$  mmHg
- high diastolic blood pressure:  $> 105$  mmHg and an increase of  $\geq 20$  mmHg
- low heart rate:  $< 50$  bpm and a decrease of  $\geq 15$  bpm
- high heart rate:  $> 120$  bpm and an increase of  $\geq 15$  bpm

The number and percentage of patients with outlying values will be tabulated by treatment group and time interval.

No subgroup analyses will be performed.

Unscheduled vital signs data will be listed (Section 16 of the CSR) but will be included in the summary tables.

